3.0 STUDY AIMS

3.1 Aim 1

To assess the effect of the relational agent/Kardia intervention on anticoagulant adherence. We will quantify adherence to anticoagulation with (a) proportion of days covered (PDC) obtained from pharmacy data, and (b) self-report, at 4, 8, and 12 months. Hypothesis: Intervention participants will have better anticoagulant adherence than control arm participants as measured by objective and self-reported assessments of adherence.

3.2 Aim 2

To identify the effect of the intervention on health care utilization (HCU). We will quantify 12month HCU for intervention administration. Hypothesis: Intervention participants will have lower HCU events compared to control arm participants.

3.3 Aim 3

To determine the effect of the intervention on HRQoL and symptoms. We will compare HRQoL and symptoms between the intervention and control arms at 4, 8, and 12 months with the AF Effect on QualiTy of life (AFEQT) instrument (specific to HRQoL in AF) and the Patient-Reported Outcomes Measurement Information System (PROMIS)-29 Profile. Hypothesis:

Intervention participants will have superior HRQoL and lower symptom burden compared to control arm participants at 4, 8, and 12 months.

3.4 Aim 4

To examine mechanisms for the effect of the intervention. We will determine how patientcentered baseline factors including sex, race, health literacy, AF classification (paroxysmal versus chronic), and symptom burden moderate the intervention effect, and how intervention engagement and use, change in symptom burden, and AF therapies mediate the intervention effect on our primary and secondary outcomes.

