analyses. We will analyze PDC as continuous (range 0-1, higher ratio indicating better adherence) and binary (optimally adherent if ≥0.8) variables. We will assess differences between the 2 study arms in PDC at 12 months with linear regression (for continuous PDC) or logistic regression (for binary PDC) adjusting for trial stratification factor (as suggested by Kahan and Morris³⁷). We will conduct our secondary assessments of adherence at 4 8, and 12 months similarly. We will categorize individuals scoring ≥ 2 on any of the 3 self-report adherence items (range 1-5, Voils et al.³⁸) as nonadherent. To assess whether the effect of the intervention changes over time, we will use linear (for continuous measures) or non-linear (for categorical measures) mixed-effect models with random intercepts with adherence measures modeled as a function of study arm, study visit and their interaction. We calculated the statistical power to detect a range of difference in PDC (our primary outcome) between the intervention and control arms. After accounting for 10% attrition through 12 months (consistent with our prior RCTs), we determined that a sample size of 119 in each study arm will enable us to detect a minimum difference in PDC between the two groups as small as 11.7% with 85% power (assuming a SD=30%). Our power calculations assume use of 2-sided tests with 0.05 significance level. With an additional, unexpected 10% attrition (n=106 per arm, to accommodate for relocation, loss-to- follow-up, institutionalization, or death), we will be able to detect a minimum difference in PDC as small as 12.4% (0.41 standardized mean difference) with 85% power. Both are considered small effect sizes per Cohen's guidelines.³⁹

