Medical records will be reviewed to assess health care utilization (emergency visit, hospitalization, and number of days hospitalized). Participants will complete assessments and questionnaires identical to several of those done at the baseline and month 4 visits.

4th Study follow-up: - +~12 months

The 4th follow up will be conducted over the phone by trained interviewers. Participants will complete assessments and questionnaires identical to several of those done at the baseline and month 4 and 8 visits. Medical records will be reviewed to assess health care utilization (emergency visit, hospitalization, and number of days hospitalized).

At time- +~12 months

Medication fill data, for purposes of calculating the proportion of days covered (PDC), a common measure of medication adherence, will also be extracted from the EHR and from the pharmacist(s). Study staff will assess the EHR for incidence of adverse cardiovascular event and mortality. Study staff will also use the National Death Index to identify participant deaths and their dates.

10 Clinical Trial Oversight and Monitoring

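### The random-intercept-only model for change in PDC effect over time has no safeguard: a 12 v 4 month contrast could reject about 7-14% under the null, the joint interaction test about 5-7%

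*Combined protocol and SAP*

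**What the plan says.** Section 5.0, Statistical approach for Aim 1, gives the primary analysis as "differences between the 2 study arms in PDC at 12 months with linear regression", or logistic regression for binary PDC. The secondary comparisons at each visit are done the same way.

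A separate model has a separate purpose: "To assess whether the effect of the intervention changes over time". It is linear for continuous and non-linear for categorical measures, and is specified as "mixed-effect models with random intercepts with adherence measures modeled as a function of study arm, study visit and their interaction". No random slope, other residual covariance or robust standard error is named. The plan does not say whether visit is categorical or linear, or whether the interaction is tested jointly or through a particular contrast.

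On the data, section 3.1 plans "proportion of days covered (PDC) obtained from pharmacy data, and (b) self-report, at 4, 8, and 12 months". Table 1 in section 8.1 lists PDC at 12 months only. The follow-up schedule (section 9) has fill data extracted at about 12 months. No section says whether PDC at 4, 8 and 12 months is cumulative from randomisation or computed per 4-month window.

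**The concern.** In a linear mixed model, a random intercept with independent residuals implies compound symmetry: the same variance at each visit and the same correlation between every pair of visits. The model then applies one pooled variance to every between-visit difference.

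Pharmacy-fill adherence is a poor candidate for that structure. Cumulative windows overlap, so later values contain earlier ones. With separate windows, a patient who stops tends to stay stopped, so neighbouring windows should be more alike than distant ones. In both cases the pooled variance tends to be too small for 12 v 4 months and too large for 12 v 8 months.

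The intervention lasts 4 months and the later visits are there to judge sustainability. A comparison of the 12-month effect with the 4-month effect is therefore the natural follow-up, and it is the contrast most exposed to a false finding of change. The 12 v 8 contrast is exposed to the opposite error.

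**Working it through.** **Inputs from the documents.** 119 evaluable per arm, SD 30 percentage points, 85% power, "2-sided tests with 0.05 significance level" (stated for the power calculations and taken here as the nominal level), three post-randomisation visits. **Assumed, because not given:** the PDC windows and the within-person covariance. A range is shown.

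**1. The plan's own figure.** Detectable difference = (1.960 + 1.036) × 30 × √(2/119) = 11.65 by the normal formula, or 11.70 with the t distribution. With 106 per arm it is 12.35 or 12.40. The stated 11.7% and 12.4% reproduce. They concern the 12-month regression, not this model.

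**2. What the model does.** In balanced data the random-intercept fit uses the average of the three pairwise difference variances for every contrast. Let r be the true variance of a contrast divided by the model's variance. Type I error is then 2[1 − Φ(1.96/√r)]. With three equally spaced visits, a linear trend is the same contrast as 12 v 4.

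**3. Cumulative PDC from equally correlated windows.** Write the window values as W1, W2, W3. PDC is W1, then (W1+W2)/2, then (W1+W2+W3)/3. The differences have these weights and relative variances, whatever the correlation:

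- 12 v 4: (−2/3, 1/3, 1/3), giving 2/3
- 8 v 4: (−1/2, 1/2, 0), giving 1/2
- 12 v 8: (−1/6, −1/6, 1/3), giving 1/6

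The average is (2/3 + 1/2 + 1/6)/3 = 4/9. For 12 v 4, r = (2/3)/(4/9) = 1.5. The model SE is √(2/3) = 0.82 of the truth and the error is 2[1 − Φ(1.600)] = 11.0%. For 12 v 8, the model SE is √((4/9)/(1/6)) = 1.63 times the truth, and the test rejects 0.1% under the null. A 12 v 8 contrast with 80% power on the correct SE would have about 1 − Φ(1.96 × 1.633 − 2.80) ≈ 34%.

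**4. Separate windows with AR(1) correlation ρ.** Adjacent differences have variance proportional to 2(1−ρ), and 12 v 4 to 2(1−ρ²). Hence r = 3(1+ρ)/(3+ρ) for 12 v 4. At ρ = 0.5, r = 4.5/3.5 = 1.286 and the error is 8.4%. The 12 v 8 SE is too large by a factor √((3+ρ)/3), which is 1.08 at ρ = 0.5 and 1.14 at ρ = 0.9.

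**5. Range of structures, null rejection rate (%).** The joint 2-df test is a weighted chi-square mixture.

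| Assumed structure | r, 12 v 4 | 12 v 4 | Joint 2-df | 12 v 8 |
|---|---|---|---|---|
| Compound symmetry | 1.00 | 5.0 | 5.0 | 5.0 |
| Separate, AR(1) 0.3 | 1.18 | 7.1 | 5.1 | 4.0 |
| Separate, AR(1) 0.5 | 1.29 | 8.4 | 5.3 | 3.4 |
| Separate, AR(1) 0.9 | 1.46 | 10.5 | 5.8 | 2.5 |
| Separate, AR(1) 0.5-0.9 plus 20% noise | 1.16-1.23 | 6.9-7.7 | 5.1-5.2 | 3.7-4.1 |
| Random slope, variance 0.05-1 × residual | 1.05-1.50 | 5.6-11.0 | 5.0-6.0 | 4.7-2.4 |
| Cumulative, equally correlated windows | 1.50 | 11.0 | 6.6 | 0.1 |
| Cumulative, AR(1) windows 0.9 | 1.75 | 13.8 | 7.2 | 0.3 |

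The limit, when all within-person change is linear, is r = 2. That gives 16.6% for 12 v 4 and 8.3% for the joint test.

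**6. Checks by simulation.** With 40,000 null trials per structure at 119 per arm, the 12 v 4 error was 4.9% under compound symmetry, 8.2-10.5% for AR(1) 0.5-0.9 and 10.8-13.8% for cumulative PDC. REML fits at 132 per arm with dropout to 10% (1,000-2,000 per structure) gave 8.8-11.3% for 12 v 4 and 4.8-6.4% for the joint test under the non-exchangeable structures.

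**7. With an unstructured covariance.** The same 40,000-trial runs gave 4.9-5.1% for 12 v 4 and 4.8-5.2% for the joint test under every structure tried.

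**The case against.** The strongest reply is that the plan names no 12 v 4 contrast. With visit categorical, the usual test of an arm-by-visit interaction is joint, and that test is only mildly inflated: 5-7% across most structures, and no more than about 8.3% in balanced data. This stands. A reader might infer that the plan's test of change over time rejects 8-14% under the null. The documents do not support that, because those rates belong to a contrast or trend that they leave unspecified.

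Second, a reader might infer that serial PDC is known to violate compound symmetry. That is arithmetic only if PDC is cumulative. A full year of pharmacy records (section 7.3) and extraction at about 12 months fit a cumulative measure, but no section states one. For separate windows the violation is plausible, not shown, and mild structures give 5-8%. This also stands.

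Third, Table 1 schedules PDC at 12 months only, so it is uncertain how far serial PDC will be analysed, although section 3.1 plans it. Self-report and dichotomised PDC go through the non-linear models, for which nothing was calculated here.

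Fourth, whether an effect exists at a given visit is tested by visit-specific regressions that do not use this covariance. That is correct, and it confines the point to one supporting analysis.

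None of this supplies a reason to keep the restrictive covariance. Even with the joint test, intervals for individual visit contrasts would come from the same pooled variance.

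**Conclusion.** The point holds for continuous PDC in the change-over-time analysis. The random-intercept-only covariance is unsafeguarded and ill-suited to the outcome. Under assumed decaying or cumulative correlation, a 12 v 4 contrast or linear trend would reject about 7-14% under the null and the joint test about 5-7%. The 12 v 8 standard error would be too large, by 63% in the cumulative, equally correlated case. A weak random slope gives less (5.6%), and true compound symmetry gives no error. The sizes depend on windows and correlations that the documents do not give.

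A reader might go further and doubt the main result. The documents give no ground for that: the 12-month regression does not use this model, and its power figures reproduce. This is a worthwhile improvement to a secondary analysis, not a threat to the primary conclusion.

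**What to change.** In section 5.0, Statistical approach for Aim 1:

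- For continuous PDC, replace the random-intercept specification by a repeated-measures model with visit categorical and an unstructured within-person covariance across the three visits, fitted by REML with Kenward-Roger or Satterthwaite degrees of freedom.
- Name the joint arm-by-visit test, and the 12 v 4 and 12 v 8 month contrasts to be reported with it.
- State whether PDC at 4, 8 and 12 months is cumulative or per window, and align Table 1 with section 3.1. If PDC is cumulative, overlap dilutes 12 v 4 as a measure of fading under any covariance, so the definition matters in its own right.

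No change is proposed for the categorical measures. Robust standard errors would not by themselves repair misspecified random effects in a non-linear mixed model, and no calculation here bears on them.

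The cost is a few sentences. Six covariance parameters are estimated from about 238 people (2 × 119). If compound symmetry were true after all, the critical value for 12 v 4 would move only from 1.965 (472 df) to 1.970 (236 df).

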4. STUDY DESIGN

4.1 Study Overview

This is a randomized clinical trial to evaluate the effect of a smartphone-based intervention on health outcomes in people with the heart disease called atrial fibrillation. The study will enroll 264 patients residing in rural municipalities (defined as "rural" by the Center for Medicaid and Medicare Services Rural Health Clinics Program) with this condition and randomize them to the intervention or control. Intervention participants will receive a smartphone with an application (or app) called a relational agent, which simulates conversation. In addition, they will receive an AliveCor Kardia for heart rate and rhythm monitoring, an FDA-approved, widely used instrument that pairs with the smartphone. Control participants will receive a smartphone with a general health application (WebMD) and they will not receive an AliveCor Kardia device. The intervention will last 4 months and participants will have visits at baseline, 4, 8 and 12 months. The study will evaluate the improvement in quality of life, medical adherence and health care utilization resulting from the intervention.

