5.0 STATISTICAL CONSIDERATIONS

We propose a two-arm RCT to evaluate the efficacy of the relational agent and AliveCor Kardia heart rhythm monitor to improve patient-centered outcomes in patients with the debilitating chronic condition atrial fibrillation (AF). We will recruit 264 patients with AF receiving anticoagulation over a 30-month period, prioritizing recruitment in socioeconomically depressed regions in rural Northwest Pennsylvania. We will randomize participants 1:1 to receive the mobile relational agent and Kardia (n=132) or control (n=132) for 4 months, conducting randomization with a web-based data management system that we have used in prior RCTs. Randomization will be stratified by type of oral anticoagulant (warfarin or direct acting oral anticoagulant). We will assess the impact of our intervention at 4, 8 months and then at 12 months to determine sustainability. Our primary hypothesis will test whether the relational agent and Kardia intervention can improve adherence to anticoagulation as quantified by the PDC and by participant self- report. Our secondary hypotheses will evaluate 1) assessments of health care utilization between the intervention and control; 2) the improvement in health-related quality of life at 4, 8, and 12 months compared to the control, as measured by instruments specific to AF and general, validated quality of life assessments; and 3) the mechanisms for the effect of the intervention, as evaluated by assessments of moderation and mediation. All participants will have return visits at 4, 8, and 12 months. The outcomes will all be calculated without reference to intervention arm. We will use the intention-to-treat principle for all primary and secondary analysis. All analyses will be blinded to trial randomization arm.

Statistical approach for Aim 1. The primary outcome for Aim 1 is anticoagulant adherence as assessed by PDC. We will use the intention-to-treat principle for all primary and secondary

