Statistical approach for Aim 2. We will compare HCU across trial arms in models that again account for trial stratification factor.³⁷ We will use the electronic health record (EHR) in concert with 4-, 8-, and 12-month self-report to catalog events (hospitalization, emergency room and ambulatory visits, medications, and procedures) and classify them as related to AF. We will determine person-year of follow-up as starting from the date of randomization to the 12-month visit. We will then classify HCU in aggregate and by item as count outcomes. We will use generalized estimating equations (GEE) negative binomial regression models (chosen instead of Poisson regression due to expected over-dispersion in the data). Similar approaches will be used to assess counts for each HCU component. Based on preliminary data from an outpatient registry of individuals with chronic AF, we expect there will be 42.0 events for every 100 person-years in the control arm of the trial.⁴⁰We estimate that we have 85% power to detect a minimum absolute reduction of 21 events per 100 person-years in the intervention group, assuming an equivalent number of events in the control group at 12 months with a sample size of 132 per arm. A 20% attrition in study participation (n=106 per arm) at 12 months will still allow us to detect a minimum of absolute reduction of 23 events per 100 person-years in the intervention group with 85% statistical power. As exploratory analyses, we will perform survival analyses to compare the time to event between the intervention and control arms for preselected outcomes: AF-related hospitalization, emergency visit, or procedure; myocardial infarction; heart failure; stroke; and allcause mortality. Participants will contribute 18 to 51 months of follow-up: those without the event of interest will be censored at the end of follow-up. We will examine the assumption of proportional hazards and use Cox regression models to estimate the hazards ratio for assigned treatment for each outcome.

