7.6 Blinding

This is a parallel-arm, randomized clinical trial. Neither the study participants nor the study staff will be blinded to assignment to intervention or control arm. The baseline and 4-follow-up visits will be completed either in person or over the phone with a study staff member.

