10.1 Data Safety Monitoring

This study will recruit subjects at the University of Pittsburgh Medical Center (UPMC) who have a chronic heart rhythm disease, atrial fibrillation (AF), and are receiving anticoagulation for stroke prevention. Participants are expected to constitute a high-risk population, as they will live in rural settings, have limited socioeconomic resources, and likely have low health literacy. The study will consist of 264 adults who will be randomized to an intervention or control cohort. The intervention cohort will receive (1) a smartphone with a relational agent application, described in the application as an embodied conversational agent, and (2) the AliveCor Kardia heart rate and rhythm monitor (described here as Kardia for simplicity). Topics and content provided by the relational agent will focus on selfcare in AF, including symptom monitoring, maintenance, and health-promoting behaviors. The relational agent will also provide education about AF and its treatments and outcomes, and health-related quality of life. The Kardia is an FDA-approved device that also uses the smartphone. It provides 30 continuous seconds of ECG monitoring similar to a Lead I rhythm strip of a 12-lead ECG. Both devices are non-invasive and may be described as smartphone applications, or apps. Participants randomized to the control arm will receive an educational session about AF and a smartphone with the WebMD application installed. participants will use the intervention for 4 months and have return visits at 4-, 8- and 12-months with assessments as documented in the application. Intervention participants will use the smartphone in order to have interactive exchanges with the relational agent and to check their heart rates and rhythm with the Kardia. The study team will follow up on the results of the smartphone agent and the Kardia, as these mobile health applications can provide important information that can be used to guide and enhance patient care. If results meet specified criteria, then the study team will send alerts through the electronic health record to the physicians and care teams that provide care for intervention participants. The research questions being investigated by this study consequently have direct implications for clinical care and patient management.

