Risk assessment. Participation in the proposed research may be considered moderate risk. This is because (1) the investigation may have direct implications for clinical care; (2) findings identified by use of the relational agent and Kardia may enter the electronic health record and thereby result in modified care; and (3) recruitment of high-risk populations (i.e., individuals with limited socioeconomic resources, low health literacy, and/or racial/ethnic minorities). As stated in the Informed Consent, use of the relational agent does not replace routine, urgent, or emergent clinical care. Participants in this trial will be instructed NOT to delay seeking care because they are using the relational agent to address a medical problem, question, concern or issue. All AE will be closely evaluated in order to ascertain if the AE is related or possibly related to participation in this research. Participant use of the relational agent and Kardia in proximity to the AE will be scrutinized for whether or not use of the intervention delays participants from seeking care. If necessary, participants will be directly interviewed to appreciate their understanding of the relation of their participation in this research and the occurrence of the AE. The project manager, coinvestigators, and PI will review the AE and evaluate for their association with the intervention. The results of such examination will be recorded on a unique report form as prepared by the Epidemiology Data Center and submitted routinely for review to the DSMB.

An additional risk for participants is loss of confidentiality. The risk of breach of confidentiality is best addressed by appropriate study procedures. The PI will be responsible for assuring that study procedures are adhered to regarding data security, transfer, and communications in tracking participants by meeting regularly with study staff, reviewing procedures and performing quality control reviews of study forms.

Data and safety monitoring for continuation, modification, or termination of participation or the clinical trial. The DSMB will review summaries of AEs, SAEs, and Unanticipated Problems and make recommendations for the continuation, modification or termination of the trial. The trial is not expected to have an early termination.

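### AF-relatedness of utilisation events has no stated rule, classifier or masking, while study staff know the arm and Kardia/agent alerts enter intervention records only

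*Combined protocol and SAP*

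**What the plan says.** All references are to the combined protocol and SAP.

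- **Section 5.0, Aim 2.** Working from the EHR and the 4-, 8- and 12-month self-reports, the team will "catalog events (hospitalization, emergency room and ambulatory visits, medications, and procedures) and classify them as related to AF". Utilisation is then analysed as counts, in aggregate and by item. An exploratory Cox analysis includes time to AF-related hospitalisation, emergency visit or procedure.
- **Section 5.0, opening paragraph.** Two assurances are given: "The outcomes will all be calculated without reference to intervention arm" and "All analyses will be blinded to trial randomization arm".
- **Section 7.6.** "Neither the study participants nor the study staff will be blinded to assignment to intervention or control arm". No exception is made for outcome assessors.
- **Section 10.1.** Alerting is conditional on the findings: "then the study team will send alerts through the electronic health record to the physicians and care teams that provide care for intervention participants".
- **Section 10.3, risk assessment.** It is expected that "findings identified by use of the relational agent and Kardia may enter the electronic health record and thereby result in modified care".
- **Section 4.1.** Of control participants: "they will not receive an AliveCor Kardia device".
- **Sections 7.7 and 9.** The principal investigator reviews the Kardia results. Study phones come back at the 4-month visit. At about 12 months, study staff search the EHR for cardiovascular events and deaths.

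**The concern.** Whether a hospital stay, visit, drug or procedure is related to AF is a judgement unless a rule fixes it. Here there is no rule. The people most likely to make the judgement may know the arm, and the record they read can contain trial-generated rhythm findings and alerts in one arm only.

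Two mechanisms follow, and they need not point the same way. Extra Kardia or agent documentation can make an intervention-arm event look more AF-related than the same event would look in a control record. Expectation of benefit can make a classifier who knows the arm less ready to call an intervention event AF-related.

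At stake are the AF-related utilisation counts (utilisation is a secondary outcome) and the exploratory AF-related time-to-event outcome. Section 5.0 does not say whether aggregate utilisation, or the 42.0 events per 100 person-years used for power, is all-cause or AF-related. A reader therefore cannot tell whether the main utilisation comparison rests on this judgement.

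**Working it through.** **Step 1. Set the passages side by side.**

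| Question | What the documents give |
|---|---|
| Who classifies? | Section 5.0 uses the first-person plural; section 8.1.15 names no abstractor |
| By what rule? | None stated |
| Masked? | No masking or redaction of the record described; staff unblinded (7.6) |
| Same source record in both arms? | Routine care records in both; Kardia/agent alerts and findings in intervention records only (4.1, 10.1, 10.3) |
| Assurance | Outcomes calculated without reference to arm (5.0) |

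The assurance has no mechanism behind it for this step.

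**Step 2. Reproduce the plan's own figure.** This is the only figure attached to the endpoint. Inputs from section 5.0: control rate 0.42 per person-year, reduction 0.21, 132 per arm, two-sided 0.05 (stated under Aim 1, taken to apply here). Assumed: about one person-year each and Poisson variance.

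- SE of the log rate ratio = √[(1/0.42 + 1/0.21)/132] = 0.2326.
- z = ln(2)/0.2326 = 2.980; power = Φ(2.980 − 1.960) = 84.6%.

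This agrees with the stated 85%. Masked classification would not alter this figure.

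**Step 3. Rate ratio from classification alone.** Let s be the share of events truly AF-related, and m the fraction of the other events called AF-related in the intervention arm only. With no true effect, RR = [s + m(1 − s)]/s. Both s and m are assumed. The last column confines the relabelling to 4 of 12 months with even event timing: 1 + (RR − 1)/3.

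| s | m | RR, 12 months | RR, 4 of 12 months |
|---|---|---|---|
| 0.5 | 0.10 | 1.10 | 1.03 |
| 0.5 | 0.20 | 1.20 | 1.07 |
| 0.3 | 0.10 | 1.23 | 1.08 |
| 0.3 | 0.20 | 1.47 | 1.16 |

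**Step 4. Effect on the test.** Assume that the 42.0 per 100 person-years are the events being classified, with Poisson variance and 132 per arm. With no true effect and an observed ratio r, d = ln(r)/√[(1/0.42 + 1/(0.42r))/132], and the two-sided rejection rate is 1 − Φ(1.96 − d) + Φ(−1.96 − d).

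| Distortion of the intervention-arm rate | Rejection if over-classified | Rejection if under-classified |
|---|---|---|
| 5% | 5.8% | 5.8% |
| 10% | 8.1% | 8.4% |
| 20% | 17.1% | 19.8% |
| 30% | 31.2% | 39.9% |

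For example, r = 1.20 gives d = 0.1823/0.1818 = 1.003 and 17.1%. At r = 1.067 (the 20% case confined to 4 months), d = 0.0645/0.1869 = 0.345 and the rate is 6.4%. Under-classification errs in favour of the intervention.

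With a true ratio of 0.50, over-classification by 10% moves the observed ratio to 0.55 and power from 84.6% to 75.5%. Over-classification by 20% moves them to 0.60 and 64.4%.

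**The case against.** **The classifier is not named.** A reader might infer that the plan assigns this task to unblinded staff. It does not say so. The section 9 sentence about study staff searching the EHR concerns cardiovascular events and mortality. The data-management text after section 10.3 gives dataset preparation to the coordinating center's programmer and analyst, and defers procedural detail to a Manual of Operations that is not among the documents. This stands: the classifier's knowledge of arm is inferred from section 7.6 and from the absence of any blinded assessor.

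**There may be no contradiction.** A reader might also conclude that the section 5.0 assurance is false. It may cover only the later derivation and analysis of counts, and some staff knowing the arm does not prove that the arm is used. This stands too. On that reading, however, the classification step has no stated protection at all.

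**The records differ less than it seems.** It would be wrong to say that only intervention records hold rhythm findings. Section 6.2 has AF confirmed by ECG, Holter or clinical note in everyone, and routine care continues in both arms. Alerts are conditional, and new ones should largely stop once phones are returned at about 4 months. This limits the record-based mechanism, as the last column of Step 3 shows. It does not limit staff knowledge of arm, which lasts all year.

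**Some extra AF-related care may be real.** Section 10.3 expects modified care, and Aim 4 treats EHR alerts as a mediator. A true rise in AF-related encounters is an effect of the intervention. Without a fixed rule, though, it cannot be told apart from relabelling.

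**It is not the primary outcome.** Correct. PDC comes from fill data, and the AF-related Cox analysis is labelled exploratory.

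**Conclusion.** The point holds as a gap between an assurance and the process described. Events are to be classified as AF-related with no stated rule, classifier or masking, in a trial whose staff are unblinded and whose intervention records alone can carry Kardia or agent alerts and findings. Nothing in the plan shows how the section 5.0 assurance is met for this step.

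The bias could go either way, and its size is not known. The ratios in Step 3 (1.03 to 1.47) and the rejection rates in Step 4 rest on assumed shares and misclassification rates. They show only that moderate differential classification would matter. Step 4 also assumes that the 42.0 rate counts the classified events, which the documents do not establish.

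The documents do not support the inference that the trial's main result is at risk. PDC and all-cause utilisation counts do not depend on this judgement. This is an inexpensive improvement to a secondary and an exploratory outcome.

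**What to change.** 1. Prespecify an AF-relatedness rule based on the principal encounter diagnosis or procedure code. Have the data coordinating center apply it to files without arm, Kardia or alert fields.
2. For events outside the UPMC system (sections 7.3 and 8.1.15), apply the same rule to redacted discharge records. For medications, which have no encounter diagnosis, use a prespecified drug-class list.
3. Report all-cause hospitalisation and emergency-visit counts alongside, as a check that does not depend on classification. The main utilisation endpoint need not change.
4. State whether aggregate utilisation and the 42.0 rate are all-cause or AF-related.
5. If masked classification is not adopted, qualify the section 5.0 assurance for this outcome.

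**Cost.** A code list, a drug-class list, SAP wording and redaction of outside records. The sample size does not change and no extra assessor is needed.

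**Downsides.** Codes are coarser than chart review. Codes entered by clinicians who saw an alert can still carry some arm effect, so the rule reduces the bias but does not remove it. This is why the all-cause counts should be shown next to it.
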